### C. ADDITIONAL PRINCIPLES FOR MEDICAL RESEARCH COMBINED WITH MEDICAL CARE

31. The physician may combine medical research with medical care only to the extent that the research is justified by its potential preventive, diagnostic or therapeutic value and if the physician has good reason to believe that participation in the research study will not adversely affect the health of the patients who serve as research subjects.
32. The benefits, risks, burdens and effectiveness of a new intervention must be tested against those of the best current proven intervention, except in the following circumstances:
33. The use of placebo, or no treatment, is acceptable in studies where no current proven intervention exists; or
34. Where for compelling and scientifically sound methodological reasons the use of placebo is necessary to determine the efficacy or safety of an intervention and the patients who receive placebo or no treatment will not be subject to any risk of serious or irreversible harm. Extreme care must be taken to avoid abuse of this option.
35. At the conclusion of the study, patients entered into the study are entitled to be informed about the outcome of the study and to share any benefits that result from it, for example, access to interventions identified as beneficial in the study or to other appropriate care or benefits.
36. The physician must fully inform the patient which aspects of the care are related to the research. The refusal of a patient to participate in a study or the patient's decision to withdraw from the study must never interfere with the patient-physician relationship.

37. In the treatment of a patient, where proven interventions do not exist or have been ineffective, the physician, after seeking expert advice, with informed consent from the patient or a legally authorized representative, may use an unproven intervention if in the physician's judgement it offers hope of saving life, re-establishing health or alleviating suffering. Where possible, this intervention should be made the object of research, designed to evaluate its safety and efficacy. In all cases, new information should be recorded and, where appropriate, made publicly available.

22.10.2008

## **Appendix III**

U.S. Prescribing Information for CORTROSYN® (cosyntroin) for injection

**CORTROSYN®™**  
**FOR DIAGNOSTIC USE ONLY**  
(cosyntroin) for Injection

**DESCRIPTION**

CORTROSYN™ (cosyntroin) for Injection is a sterile lyophilized powder in vials containing 0.25 mg of CORTROSYN™ and 10 mg of mannitol to be reconstituted with 1 mL of 0.9% Sodium Chloride Injection, USP. Administration is by intravenous or intramuscular injection. Cosyntroin is  $\alpha$  1 - 24 corticotroin, a synthetic subunit of ACTH. It is an open chain polypeptide containing, from the N terminus, the first 24 of the 39 amino acids of natural ACTH. The sequence of amino acids in the 1 - 24 compound is as follows:

Ser - Tyr - Ser - Met - Glu - His - Phe - Arg - Trp - Gly - Lys - Pro - Val - Gly - Lys - Lys - Arg - Arg - Pro - Val - Lys - Val - Tyr - Pro  
1 2 3 4 5 6 7 8 9 10 11 12 13 14 15 16 17 18 19 20 21 22 23 24

**CLINICAL PHARMACOLOGY**

CORTROSYN™ (cosyntroin) for Injection exhibits the full cortico-steroidogenic activity of natural ACTH. Various studies have shown that the biologic activity of ACTH resides in the N-terminal portion of the molecule and that the 1 - 20 amino acid residue is the minimal sequence retaining full activity. Partial or complete loss of activity is noted with progressive shortening of the chain beyond 20 amino acid residues. For example, the decrement from 20 to 19 results in a 70% loss of potency.

The pharmacologic profile of CORTROSYN™ is similar to that of purified natural ACTH. It has been established that 0.25 mg of CORTROSYN™ will stimulate the adrenal cortex maximally and to the same extent as 25 units of natural ACTH. This dose of CORTROSYN™ will produce maximal secretion of 17-OH corticosteroids, 17- ketosteroids and / or 17 - ketogenic steroids.

The extra-adrenal effects which natural ACTH and CORTROSYN™ have in common include increased melanotropic activity, increased growth hormone secretion and an adipokinetic effect. These are considered to be without physiological or clinical significance.

Animal, human and synthetic ACTH (1-39) which all contain 39 amino acids exhibit similar immunologic activity. This activity resides in the C-terminal portion of the molecule and the 22-39 amino acid residues exhibit the greatest degree of antigenicity. In contrast, synthetic poly-peptides containing 1-19 or fewer amino acids have no detectable immunologic activity. Those containing 1-26, 1-24 or 1-23 amino acids have very little immunologic although full biologic activity. This property of CORTROSYN™ assumes added importance in view of the known antigenicity of natural ACTH.

## **INDICATIONS AND USAGE**

CORTROSYN™ (cosyntropin) for Injection is intended for use as a diagnostic agent in the screening of patients presumed to have adrenocortical insufficiency. Because of its rapid effect on the adrenal cortex it may be utilized to perform a 30-minute test of adrenal function (plasma cortisol response) as an office or outpatient procedure, using only 2 venipunctures (see DOSAGE AND ADMINISTRATION section).

Severe hypofunction of the pituitary - adrenal axis is usually associated with subnormal plasma cortisol values but a low basal level is not per se evidence of adrenal insufficiency and does not suffice to make the diagnosis. Many patients with proven insufficiency will have normal basal levels and will develop signs of insufficiency only when stressed. For this reason a criterion which should be used in establishing the diagnosis is the failure to respond to adequate corticotropin stimulation. When presumptive adrenal insufficiency is diagnosed by a subnormal CORTROSYN™ test, further studies are indicated to determine if it is primary or secondary.

Primary adrenal insufficiency (Addison's disease) is the result of an intrinsic disease process, such as tuberculosis within the gland. The production of adrenocortical hormones is deficient despite high ACTH levels (feedback mechanism). Secondary or relative insufficiency arises as the result of defective production of ACTH leading in turn to disuse atrophy of the adrenal cortex. It is commonly seen, for example, as result of corticosteroid therapy, Sheehan's syndrome and pituitary tumors or ablation.

The differentiation of both types is based on the premise that a primarily defective gland cannot be stimulated by ACTH whereas a secondarily defective gland is potentially functional and will respond to adequate stimulation with ACTH. Patients selected for further study as the result of a subnormal CORTROSYN™ test should be given a 3 or 4 day course of treatment with Repository Corticotropin Injection USP and then retested. Suggested doses are 40 USP units twice daily for 4 days or 60 USP units twice daily for 3 days. Under these conditions little or no increase in plasma cortisol levels will be seen in Addison's disease whereas higher or even normal levels will be seen in cases with secondary adrenal insufficiency.

## **CONTRAINDICATION**

The only contraindication to CORTROSYN™ (cosyntropin) for Injection is a history of a previous adverse reaction to it.

## **PRECAUTIONS**

### **General**

CORTROSYN™ (cosyntropin) for Injection exhibits slight immunologic activity, does not contain animal protein and is therefore less risky to use than natural ACTH. Patients known to be sensitized to natural ACTH with markedly positive skin tests will, with few exceptions, react negatively when tested intradermally with CORTROSYN™. Most patients with a history of a previous hypersensitivity reaction to natural ACTH or a pre-existing allergic disease will tolerate CORTROSYN™. Despite this however, CORTROSYN™ is not completely devoid of immunologic activity and hypersensitivity reactions including rare anaphylaxis are possible. Therefore, the physician should be pre-pared, prior to injection, to treat any possible acute hypersensitivity reaction.

### **Drug Interactions**

Corticotropin may accentuate the electrolyte loss associated with diuretic therapy.

#### **Carcinogenesis, Mutagenesis, Impairment of Fertility**

Long term studies in animals have not been performed to evaluate carcinogenic or mutagenic potential or impairment of fertility. A study in rats noted inhibition of reproductive function like natural ACTH.

### **Pregnancy**

Pregnancy Category C. Animal reproduction studies have not been conducted with CORTROSYN™ (cosyntropin) for Injection. It is also not known whether CORTROSYN™ can cause fetal harm when administered to a pregnant woman or can affect reproduction capacity. CORTROSYN™ should be given to a pregnant woman only if clearly needed.

### **Nursing Mothers**

It is not known whether this drug is excreted in human milk. Because many drugs are excreted in human milk, caution should be exercised when CORTROSYN™ (cosyntropin) for Injection is administered to a nursing woman.

### **Pediatric Use**

(See DOSAGE AND ADMINISTRATION section.)

## **ADVERSE REACTIONS**

Since CORTROSYN®™ (cosyntropin) for Injection is intended for diagnostic and not therapeutic use, adverse reactions other than a rare hypersensitivity reaction are not anticipated. A rare hypersensitivity reaction usually associated with a pre-existing allergic disease and/or a previous reaction to natural ACTH is possible. Symptoms may include slight whealing with splotchy erythema at the injection site. There have been rare reports of anaphylactic reaction. The following adverse reactions have been reported in patients after the administration of CORTROSYN®™ and the association has been neither confirmed nor refuted:

- bradycardia
- tachycardia
- hypertension
- peripheral edema
- rash

## **DOSAGE AND ADMINISTRATION**

CORTROSYN™ (cosyntropin) for Injection may be administered intramuscularly or as a direct intravenous injection when used as a rapid screening test of adrenal function. It may also be given as an intravenous infusion over a 4 to 8 hour period to provide a greater stimulus to the adrenal glands. Doses of CORTROSYN™ 0.25 to 0.75 mg have been used in clinical studies and a maximal response noted with the smallest dose.

A suggested method for a rapid screening test of adrenal function has been described by Wood and Associates (1). A control blood sample of 6 to 7 ml is collected in a heparinized tube. Reconstitute 0.25 mg of CORTROSYN™ with 1mL of 0.9% Sodium Chloride Injection, USP and inject intramuscularly. The reconstituted drug product should be inspected visually for particulate matter and discoloration prior to injection. Reconstituted CORTROSYN™ should not be retained. In the pediatric population, aged 2 years or less, a dose of 0.125 mg will often suffice. A second blood sample is collected exactly 30 minutes later. Both blood samples should be refrigerated until sent to the laboratory for determination of the plasma cortisol response by some appropriate method. If it is not possible to send them to the laboratory or perform the fluorimetric procedure within 12 hours, then the plasma should be separated and refrigerated or frozen according to need.

Two alternative methods of administration are intravenous injection and infusion. CORTROSYN™ can be injected intravenously in 2 to 5 mL of saline over a 2-minute period. When given as an intravenous infusion: CORTROSYN™, 0.25 mg may be added to glucose

or saline solutions and given at the rate of approximately 40 micrograms per hour over a 6-hour period. It should not be added to blood or plasma as it is apt to be inactivated by enzymes. Adrenal response may be measured in the usual manner by determining urinary steroid excretion before and after treatment or by measuring plasma cortisol levels before and at the end of the infusion. The latter is preferable because the urinary steroid excretion does not always accurately reflect the adrenal or plasma cortisol response to ACTH.

The usual normal response in most cases is an approximate doubling of the basal level, provided that the basal level does not exceed the normal range. Patients receiving cortisone, hydrocortisone or spironolactone should omit their pre-test doses on the day selected for testing. Patients taking inadvertent doses of cortisone or hydrocortisone on the test day and patients taking spironolactone or women taking drugs which contain estrogen may exhibit abnormally high basal plasma cortisol levels.

A paradoxical response may be noted in the cortisone or hydrocortisone group as seen in a decrease in plasma cortisol values following a stimulating dose of CORTROSYN™. In the spironolactone or estrogen group only a normal incremental response is to be expected. Many patients with normal adrenal function, however, do not respond to the expected degree so that the following criteria have been established to denote a normal response:

1. The control plasma cortisol level should exceed 5 micrograms/100 ml.
2. The 30-minute level should show an increment of at least 7 micrograms/100 ml above the basal level.
3. The 30-minute level should exceed 18 micrograms/100 ml. Comparable figures have been reported by Greig and co-workers

Plasma cortisol levels usually peak about 45 to 60 minutes after an injection of CORTROSYN™ and some prefer the 60-minute interval for testing for this reason. While it is true that the 60-minute values are usually higher than the 30-minute values, the difference may not be significant enough in most cases to outweigh the disadvantage of a longer testing period. If the 60-minute test period is used, the criterion for a normal response is an approximate doubling of the basal plasma cortisol value.

In patients with a raised plasma bilirubin or in patients where the plasma contains free hemoglobin, falsely high fluorescence measurements will result. The test may be performed at any time during the day but because of the physiological diurnal variation of plasma cortisol the criteria listed by Wood cannot apply. It has been shown that basal plasma cortisol levels

and the post CORTROSYN™ increment exhibit diurnal changes. However, the 30-minute plasma cortisol level remains unchanged throughout the day so that only this single criterion should be used (3).

Parenteral drug products should be inspected visually for particulate matter and discoloration whenever solution and container permit. Reconstituted CORTROSYN™ should not be retained.

### **HOW SUPPLIED**

Box of 10 vials of CORTROSYN®™ (cosyntropin) for Injection 0.25 mg  
NDC # 0548-5900-00

### **Storage**

Store at 15-30°C (59-86°F).

CORTROSYN™ is intended as a single dose injection and contains no antimicrobial preservative. Any unused portion should be discarded.

### **Amphastar Pharmaceuticals, Inc.**

Rancho Cucamonga, CA 91730 U.S.A.

REV. 9-05

## **Appendix IV**

### WHO Classification of Corticosteroids

**WHO CLASSIFICATION OF TOPICAL CORTICOSTEROIDS**

Based on the Anatomical Therapeutic Chemical (ATC) classification system

**Group I: weak**Hydrocortisone  
Methylprednisolone  
Prednisolone**Group II: moderately potent**Alclometasone  
Clobetasone  
Desonide  
Flumetasone  
Fluocortin butyl  
Fluprednidene  
Hydrocortisone butyrate  
Triamcinolone**Group III: potent**Amcinonide  
Beclometasone  
Betamethasone  
Betamethasone dipropionate  
Budesonide  
Desoximetasone  
Diflorasone  
Diflucortolone  
Fluclorolone acetonide  
Fludroxycortide  
Fluocinolone acetonide  
Fluocinonide  
Fluocortolone  
Fluticasone  
Halometasone  
Mometasone  
Prednicarbate  
Ulobetasol**Group IV: very potent**Clobetasol  
Halcinonide

**Appendix V**  
Itch and Sleep Questionnaire

### **Itch and Sleep Questionnaire**

Subject CRF Number \_\_\_\_\_

Visit \_\_\_\_\_

Date \_\_\_\_\_

Please rate the intensity of your maximal itching on your scalp during the last 24 hours

No itch \_\_\_\_\_ Worst possible

Please rate the intensity of your maximal itching on your body (upper limbs, trunk and lower limbs) during the last 24 hours

No itch \_\_\_\_\_ Worst possible

Please rate your sleep loss during the last 24 hours

No sleep loss \_\_\_\_\_ Worst possible

3.1 List of Abbreviations

ACTH	Adrenocorticotrophic hormone
AE	Adverse Event
CRF	Case Report Form
CTR	Clinical Trial Report
ICH	International Conference on Harmonisation
IGA	Investigator's global assessment
LOCF	Last Observation Carried Forward
LLOQ	Lower Limit of Quantification
IMP	Investigational Medicinal Product
MedDRA	Medical Dictionary for Regulatory Activities
PASI	Psoriasis Area and Severity Index
PK	Pharmacokinetics
SAP	Statistical Analysis Plan

4 Statistical Analysis Plan Authors

PPD [REDACTED], MSc, Senior Statistician, Biostatistics, LEO Pharma A/S, DK-2750, Ballerup, Denmark, tel: +45 PPD [REDACTED], e-mail: PPD [REDACTED]@leo-pharma.com

PPD [REDACTED], MSc, Senior Statistician, Biostatistics, LEO Pharma A/S, DK-2750, Ballerup, Denmark, tel: +45 PPD [REDACTED], e-mail: PPD [REDACTED]@leo-pharma.com

PPD [REDACTED], PhD, Clinical Project Manager, Trial Management, LEO Pharma A/S, DK-2750, Ballerup, Denmark, tel: +45 PPD [REDACTED], e-mail: PPD [REDACTED]@leo-pharma.com

PPD [REDACTED], MSc, Principal Medical Writer, Medical Communication, LEO Pharma A/S, DK-2750, Ballerup, Denmark, tel: +45 PPD [REDACTED], e-mail: PPD [REDACTED]@leo-pharma.com

PPD [REDACTED], MD PhD, Principal Medical Expert, Medical Department, LEO Pharma A/S, DK-2750, Ballerup, Denmark, tel: +45 PPD [REDACTED], e-mail: PPD [REDACTED]@leo-pharma.com

5 Introduction

The statistical analysis will be performed as outlined in the Consolidated Clinical Study Protocol. This Statistical Analysis Plan, prepared after review of the data, contains a more technical and detailed elaboration of some points in the statistical analysis described in the

protocol. Minor deviations from the planned data presentation and analysis are accounted for. The analysis sets which are to be used for the statistical analysis are presented in Analysis Set Definition Document.

Table 1 includes protocol amendments that are relevant to the statistical reporting. The inclusion criteria for subjects *not* performed HPA and PK assessments has been updated in Consolidated Clinical Study Protocol, version 4.0, dated 16-Feb-2015. The extent of psoriasis required on the body and the severity of psoriasis required on the body and the scalp has been revised to better reflect psoriasis commonly seen in the adolescent population. The definition of ‘controlled disease’ under the secondary response criteria was updated accordingly. More details can be found in LP0076-1017 Summary of Amendment(s) to a Clinical Trial Authorisation, 02-Mar-2015 (v1.0).

Table 1: Protocol amendments that are relevant to the statistical reporting.

Section no in Consolidated Clinical Study Protocol version 4.0 and 6.0	To	From :
10.4.1.3 (a and b, BODY) The inclusion criteria for subjects not performing HPA and PK assessments was updated.	At SV2 and Visit 1, a clinical diagnosis of body (trunk and/or limbs) psoriasis which is: a. more than or equal to 3% of the body surface area (excluding psoriatic lesions of the face and sensitive areas), and b. of at least mild severity according to the investigator’s global assessment of disease severity on the body. At SV2 and Visit 1, a clinical diagnosis of scalp psoriasis which is: a. more than or equal to 10% of the scalp area, and b. of at least mild severity according to the investigator’s global assessment of disease severity on the scalp	At SV2 and Visit 1, a clinical diagnosis of scalp and body (trunk and/or limbs) psoriasis which is: a. of an extent of 10 to 35% of the body surface area (excluding psoriatic lesions of the face and sensitive areas. Sensitive areas include armpits, groin, under the breasts and in other skin folds around the genitals and buttocks), and b. of at least moderate severity according to the investigator’s global assessment of disease severity on the body.

Trial ID: LP0076-1017	Date: 16-Mar-2018	Version: 1.0 Page 7 of 27
------------------------------	--------------------------	------------------------------

10.4.1.3 (a and b, SCALP) The inclusion criteria for subjects not performing HPA and PK assessments was updated.	At SV2 and Visit 1, a clinical diagnosis of scalp psoriasis which is: a. more than or equal to 10% of the scalp area, and b. of at least mild severity according to the investigator’s global assessment of disease severity on the scalp	At SV2 and Visit 1, a clinical diagnosis of scalp psoriasis which is: a. more than or equal to 10% of the scalp area, and b. of at least moderate severity according to the investigator’s global assessment of disease severity on the scalp.
10.10.1 Revised secondary response criteria.	Subjects with “Controlled disease” (i.e., “Clear” or “Almost clear” for subjects with at least “Moderate” disease at baseline, “Clear” for subjects with “Mild” disease at baseline) according to the investigator’s global assessment of disease severity on the body at end of treatment.	Subjects with “Controlled disease” (i.e., “Clear” or “Almost clear”) according to the investigator’s global assessment of disease severity on the body at end of treatment.

6 Statistical Analysis

The statistical analysis will be carried out as described in the Consolidated Clinical Study Protocol with a few exceptions as described below.

Lists of planned tables, figures and individual subject data listings for the Clinical Trial Report are provided in Appendix 1.

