#### Patient's Global Assessment of Disease Severity Scale

Clear	No psoriasis symptoms at all
Very mild	Very slight psoriasis symptoms, does not interfere with daily life
Mild	Slight psoriasis symptoms, interferes with daily life only occasionally
Moderate	Definite psoriasis symptoms, interferes with daily life frequently
Severe	Intense psoriasis symptoms, interferes or restricts daily life very frequently

*Note: Subjects with disease severity classified as "Clear" or "Very Mild" disease after the treatment period will be rated as having "Controlled disease".*

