#### **10.11.6 Analysis of Efficacy**

The statistical analysis of efficacy will be based on the full analysis set according to the defined response criteria.

The percentage of subjects who achieve “Controlled disease” according to the investigator’s global assessment of disease severity on the body will be presented by visit and at end of treatment. The 95% confidence interval (CI) which is based on a binomial distribution will be presented for the proportion of subjects with “Controlled disease” at end of treatment.

The percentage of subjects who achieve “Controlled disease” according to the investigator’s global assessment of disease severity on the body at end of treatment will also be tabulated by age-group, sex, centre and baseline disease severity according to the investigator’s assessment of body psoriasis.

The percentage change in PASI from baseline to each visit and to end of treatment will be summarised. The 95% CI for mean percentage change in PASI based on a normal distribution will be calculated for end of treatment.

The percentage of subjects who achieve “Controlled disease” according to the patient’s global assessment of disease severity on the body will be presented by visit and at end of treatment. The 95% CI based on a binomial distribution will be calculated for the proportion of subjects with “Controlled disease” at end of treatment.

The percentage of subjects who achieve “Controlled disease” according to the investigator’s global assessment of disease severity on the scalp will be presented by visit and at end of treatment.

The percentage of subjects who achieve “Controlled disease” according to the patient’s global assessment of disease severity on the scalp will be presented by visit and at end of treatment.

The investigator’s global assessment of disease severity on the body and on the scalp, PASI and patient’s global assessment of disease severity on the body and on the scalp will be summarised by visit and at end of treatment.

Patient’s assessment of itching and sleep will be summarised by visit and at end of treatment. In addition, the change from baseline to each visit and end of treatment will be summarised.

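### SAP Table 1 admits mild disease but makes controlled disease baseline-dependent for body IGA only; the scalp and patient-rated rules in the documents still ignore baseline

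*SAP*

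**What the plan says.** SAP Section 5 introduces its list of changes with "Table 1 includes protocol amendments that are relevant to the statistical reporting". For subjects not performing HPA and PK assessments, the list lowers the severity needed at SV2 and Visit 1 from moderate to "of at least mild severity according to the investigator’s global assessment of disease severity on the body" and, for the scalp, "of at least mild severity according to the investigator’s global assessment of disease severity on the scalp".

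The same section states: "The definition of ‘controlled disease’ under the secondary response criteria was updated accordingly". The row for protocol Section 10.10.1, labelled "Revised secondary response criteria", gives the new rule for body IGA. Subjects at least Moderate at baseline must reach Clear or Almost clear, and subjects Mild at baseline must reach Clear. No other definition of controlled disease appears in the list.

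For the other measures, the available rules are those of the protocol:

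- **Scalp IGA** (Section 10.8.3.1): Clear or Almost clear after treatment is controlled, whatever the baseline.
- **Patient's global assessment, body and scalp** (Section 10.8.3.2): Clear or Very mild "disease after the treatment period will be rated as having" controlled disease, whatever the baseline. Section 10.10.1 names the body version as a secondary response criterion, and Section 10.11.6 gives it a 95% CI.
- **Reporting of the scalp** (Section 10.11.6): the percentage controlled on the investigator's and on the patient's "global assessment of disease severity on the scalp will be presented by visit and at end of treatment", without a CI.

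SAP Section 6.2 refers back to the protocol's response criteria. Tables 2-12 (scalp IGA), 2-17 (patient, body) and 2-19 (patient, scalp) report the resulting rates. Only body-IGA control is tabulated by its own baseline category (Table 2-6).

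**The concern.** Admitting mild disease makes a fixed target easier to reach. The body-IGA revision deals with this by asking more of subjects who start at Mild. Scalp IGA uses the same five-point scale, and its entry threshold fell in the same amendment, yet no corresponding rule is shown.

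The patient scales have a further gap. Entry depends on the investigator's rating, so nothing stops a subject from self-rating Very mild or Clear at Visit 1. Such a subject meets the definition at end of treatment without improving.

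At stake is the reading of four rates that share one label. A reader comparing Table 2-2 with Tables 2-12, 2-17 and 2-19 would take them as measuring the same achievement. One of them, the patient-rated body rate, is a named secondary criterion with a confidence interval, and it can include subjects who did not improve.

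**Working it through.** **The plan's own figure.** Protocol Section 10.3 gives a 95% CI of about ±9% for a 30% body-IGA rate in 100 subjects. Check: 1.96 × √(0.30 × 0.70 / 100) = 0.0898, or 9.0 points. The figure reproduces. It serves below only as a yardstick.

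**Steps needed to be controlled.** Code each scale 0 (Clear), 1 (Almost clear or Very mild), 2 (Mild), 3 (Moderate), 4 (Severe). Minimum steps = baseline code − worst code that still counts as controlled.

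| Baseline | Body IGA, revised | Scalp IGA | Patient scales |
|---|---|---|---|
| Severe | 4 − 1 = 3 | 4 − 1 = 3 | 4 − 1 = 3 |
| Moderate | 3 − 1 = 2 | 3 − 1 = 2 | 3 − 1 = 2 |
| Mild | 2 − 0 = 2 | 2 − 1 = 1 | 2 − 1 = 1 |
| Almost clear / Very mild | not eligible | not eligible | 0 |
| Clear | not eligible | not eligible | 0 |

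The revised body rule keeps a two-step minimum at every eligible baseline. The other rules do not.

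**Patient scales.** Let *f* be the share of subjects at Very mild or Clear at Visit 1 and unchanged at end of treatment, and *r* the controlled rate in the rest. Reported rate = *f* + (1 − *f*)*r*. With the same denominator but those subjects not counted, the rate is (1 − *f*)*r*. The difference is *f* whatever *r* is, so each 5% contributes 5 points. Neither *f* nor *r* is in the documents. As an illustration, take *r* = 30%, borrowed from the body-IGA planning assumption:

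- *f* = 5%: 0.05 + 0.95 × 0.30 = 33.5%, against 28.5%
- *f* = 10%: 0.10 + 0.90 × 0.30 = 37.0%, against 27.0%
- *f* = 20%: 0.20 + 0.80 × 0.30 = 44.0%, against 24.0%

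SAP Table 3 shows 107 subjects assigned treatment. If all are analysed, ten such subjects contribute 10/107 = 9.3 points, about the planned half-width.

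**Scalp IGA.** Let *m* be the share Mild on the scalp at baseline and *q* the share of those ending at Almost clear. Under the body-IGA rule the scalp rate would be *m* × *q* lower. Neither input is given. SAP Table 3 shows 33 subjects with a baseline cortisol test. If all 33 had at least moderate scalp disease, as protocol Section 10.4.1.2 requires, *m* is at most (107 − 33)/107 = 74/107 = 69%. Assumed ranges, for *q* from 10% to 50%:

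- *m* = 10%: 1.0 to 5.0 points
- *m* = 25%: 2.5 to 12.5 points
- *m* = 50%: 5.0 to 25.0 points
- *m* = 69%: 6.9 to 34.6 points

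This range is too wide to serve as an estimate.

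**Carry-forward.** Protocol Section 10.11.7 takes the last recorded value up to Visit 5 as the end-of-treatment value and requires a post-baseline value only for laboratory parameters. Section 10.11.1 leaves the exclusion of subjects without later efficacy data to judgement. If such a subject were retained, a Visit 1 self-rating of Very mild could itself be carried forward as controlled.

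**The case against.** **The text that would settle the matter is missing.** The available protocol carries the criteria from before the amendment, while Table 1 cites versions 4.0 and 6.0 and Section 5 points to a separate summary of amendments. Table 1 is also visibly incomplete. It does not mention serum alkaline phosphatase, which SAP Table 3 treats as a secondary endpoint and which is absent from the protocol's secondary criteria. It also omits the assessments of psoriasis extent at Weeks 4 and 8 (Tables 2-13 to 2-15). Its silence is therefore weak evidence. This stands: a reader might infer that the sponsor decided to leave the scalp and patient rules alone, and the documents do not show that.

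**No-change control is not an effect of the amendment.** The patient scales never had an entry floor. On scalp IGA a subject cannot be controlled without change, since at least Mild is required at Visit 1. Both points stand and limit the concern.

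**A state-based definition is legitimate.** The protocol asks for both global ratings to reflect the condition at the time, and Very mild is defined by absence of interference with daily life. Nothing obliges two instruments to demand equal steps, and change is covered by PASI, itch and sleep. This is fair for the patient scales. It answers less for scalp IGA, which is the same scale as body IGA with the same lowered threshold.

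**Much of the information is already planned.** Table 1-7 gives the baseline patient rating on the body. Tables 2-11, 2-16 and 2-18 give category distributions by visit, and Listings 6-1 and 6-4 give individual ratings. What is missing is the cross-tabulation of controlled status against baseline on the same scale, which marginal distributions cannot supply.

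**Scalp control is descriptive.** It is neither a named response criterion nor given a CI, the trial is single-group, and its primary objective is safety. This stands and limits the consequence.

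**Conclusion.** The inconsistency holds on the documents as they stand. After one amendment lowered entry on body and scalp, only body IGA is shown with a baseline-dependent rule. One step from Mild counts as controlled on scalp IGA and on the patient scales. On the patient scales only, a subject already at Very mild or Clear counts with no change. The amendment did not create that second gap, but probably widened it by admitting milder disease.

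The size is unknown. A reader might infer from the illustrations that the reported rates are inflated by a definite amount. The documents do not support that, because they give no baseline counts on the scalp or patient scales. What can be said is the unit: 5 points of the patient-rated rate for each 5% of subjects already at Very mild or Clear and unchanged.

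The primary safety criteria are untouched. The interpretation of one named secondary criterion and of the scalp tabulations is affected, which is enough to justify a change that uses data already collected.

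**What to change.** Keep the protocol-defined rates as the reported results. Then:

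1. State in the SAP the rule for scalp IGA and for both patient scales, checked against protocol versions 4.0 and 6.0. If those versions already revise them, add the revisions to Table 1.
2. Print Tables 2-12, 2-17 and 2-19 by baseline category of the same scale, as Table 2-6 does for body IGA, and show the number already Clear or Very mild at baseline on the patient scales.
3. Beside each, add a rate labelled post hoc in which a baseline rating of Mild must reach Clear. On the patient scales, report subjects already Clear or Very mild at baseline separately and do not count them as responders. Merely requiring Clear from everyone at Mild or lower would not be enough, since it would still count Clear to Clear and Very mild to Clear.

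The label is needed because SAP Section 5 says the plan was written after the data had been reviewed. For the same reason the new rates should supplement the protocol-defined ones and not replace them.

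The cost is some SAP wording and a little programming, with no new data: the ratings are collected at Visit 1. The supplementary rates will be the same or somewhat lower, and the small baseline strata will be imprecise.
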